14.1 Patient numbers and power considerations

There are no data yet on PFS after 9 cycles of ixazomib citrate – thalidomide – dexamethasone induction chemotherapy. However, in the recently published MPR-R trial (Palumbo et al, NEJM. 2012; 366: 1759-69), median PFS for no-maintenance *after MPR* was 7 months. If ixazomib citrate - thalidomide – low dose dexamethasone is a more effective induction regimen, median PFS after randomization in the no-maintenance arm may be 10 months. Median PFS for lenalidomide maintenance *after MPR* was 26 months. An improvement of median PFS from 10 to 26 months with ixazomib citrate-maintenance equals a hazard ratio of 0.39. For the current sample size calculation the following assumptions have been used:

- uniform accrual for 18 months; additional follow up of 12 months after the last patient has been randomized;
- two-sided significance level a = 0.05;
- power $1 \beta = 0.90$;
- median PFS in the no-maintenance arm = 10 months:
- HR = 0.39.

This results in a total number of patients to be randomized of 94 (= 47 per arm), and the final analysis will be performed when 55 events after randomization have been reported (using the Freedman-Peto method). If we assume that 66% (based on the 34% discontinuation rate in the VISTA trial) of the patients will be randomized, then 94/0.66 = 142 patients have to be registered. However, in case the randomization rate is lower then expected, we will recalculate the number of patients that have to be registered, in order to achieve 94 randomized patients required for the primary endpoint. An estimate of the randomization rate will be performed in the first 50 patients.

Assuming a response rate of about 80% after induction chemotherapy, the 142 registered patients will enable to estimate the response rate with a standard error of about 3%.

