14.2.1 Efficacy analysis

The main endpoint will be PFS from the date of randomization. The formal test for difference in PFS between the two treatment arms will be done with a multivariate Cox regression analysis with adjustment for International Scoring System (ISS, I vs II and III), age (<75 vs ≥ 75 years) and response after induction treatment ((s)CR vs VGPR and PR). An estimate of the HR with corresponding 95% CI will be obtained. The actuarial Kaplan-Meier method will be used to estimate PFS probabilities at appropriate time points, while the Greenwood estimate will be used to construct corresponding 95% CIs. Competing risk analysis will be used to calculate cumulative incidences of PFS, progression/relapse, and death without progression (which add up to 100% at every time point). A Kaplan-Meier curve will be generated to illustrate PFS in each arm. In case the accrual will be 18 months, randomization will take place 9 months after registration of the last patient, and if 12 months of follow up after the last patient is required, then the final analysis may be performed after 18 + 9 + 12 = 39 months after start of the trial, if the complete and validated data including 55 events are available. The response rate after induction chemotherapy will be summarized as the proportion of patients with at least a PR, together with a 95% CI.

A preliminary efficacy analysis on response after induction treatment is planned when the data regarding induction treatment and response of the first 50 registered and eligible patients are available and have been evaluated. No conclusions will be drawn based on this analysis.

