15.2.2 Randomization

All patients eligible for randomization can be randomized at the HOVON Data Center by web (as described above)

The following information will be required:

- Protocol number
- Patient's study number
- Eligibility criteria

Actual dose of ixazomib given during last induction cycle

Patients will be randomized, stratified by center and response ((s)CR vs VGPR vs PR) with a minimization procedure, ensuring balance within each stratum and overall balance.

The patient study number and the result of randomization will be communicated by the HOVON Data Center by email to the pharmacy of VU University Medical Center. Ixazomib citrate or placebo will be sent for the randomized patient to the pharmacy of the site. The result of the randomization will not be conferred to caregivers, patients, or their representatives until the end of the trial.

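### The primary Cox model adjusts for induction response at two levels although minimisation balances three; aligning them is a minor, nearly free improvement

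*Protocol*

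**What the plan says.** Section 14.2.1 makes PFS from randomisation the main endpoint. It tests the arms with a Cox model adjusted for ISS (I against II and III), age (under 75 against 75 or over) and "response after induction treatment ((s)CR vs VGPR and PR" as one group. ISS is pooled in the same style in the same sentence, so two response levels are evidently intended.

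Section 15.2.2 treats response more finely: "Patients will be randomized, stratified by center and response ((s)CR vs VGPR vs PR) with a minimization procedure". Section 8.2.1 admits only patients with at least a partial response, so these three levels cover everyone randomised.

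Section 14.2.4 says that deviations made in the later SAP may touch only the exploratory analyses, and that everything except the primary analysis is hypothesis-generating. No reason is given for pooling VGPR with PR. The protocol states neither an expected response mix after induction nor an expected PFS difference between VGPR and PR.

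**The concern.** The design treats VGPR and PR as different enough to balance, while the only confirmatory test treats them as one group. If they do differ in PFS, two things follow.

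- Leaving a prognostic distinction out of a Cox model pulls the estimated hazard ratio toward 1, even when the arms are balanced on it.
- When randomisation has forced balance on that distinction, the treatment estimate varies less between trials than the model's standard error assumes. The test then rejects less often than 5% under the null.

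At stake are some attenuation of the primary estimate and some power. The usual answer, that the SAP will settle the covariate coding, is closed off by section 14.2.4. A change has to be made in the protocol.

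**Working it through.** **1. Design inputs (section 14.1).** "two-sided significance level a = 0.05"; power 0.90; "median PFS in the no-maintenance arm = 10 months"; "An improvement of median PFS from 10 to 26 months with ixazomib citrate-maintenance equals a hazard ratio of 0.39" (10/26 = 0.385, and 0.39 is used); "uniform accrual for 18 months; additional follow up of 12 months after the last patient has been randomized"; "total number of patients to be randomized of 94 (= 47 per arm"); final analysis at 55 events.

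**2. The plan's own figures reproduce.** The Freedman formula gives events = ((1 + HR)/(1 − HR))² × (z₀.₉₇₅ + z₀.₉₀)² = (1.39/0.61)² × (1.960 + 1.282)² = 5.192 × 10.507 = 54.6, i.e. 55.

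With exponential PFS, 18 months of uniform accrual and 12 more months of follow-up, P(event) = 1 − [exp(−12λ) − exp(−30λ)]/(18λ).
- Control: λ = ln 2/10 = 0.0693, giving 0.751.
- Ixazomib: λ = 0.39 × 0.0693 = 0.0270, giving 0.428.
- Mean 0.589, so 55/0.589 = 93.3, i.e. 94 patients.

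**3. Simulation of the two codings.** 94 patients, analysis at the 55th event, minimisation on centre and three-level response, Cox Wald test adjusted for ISS, age and response. The two-level and three-level models were fitted to the same data, with 12,000 trials per scenario (Monte Carlo standard error about 0.2–0.3 points).

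Assumptions not in the protocol: 30 centres; probability 0.8 of assigning the favoured arm; (s)CR-vs-VGPR hazard ratio 0.6; ISS I hazard ratio 0.7 in 25% of patients; age 75 or over hazard ratio 1.2 in 45%. The (s)CR/VGPR/PR mix is 15/40/45% in the table below.

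| PR-vs-VGPR hazard ratio | Estimated HR, 2 / 3 levels | Power at HR 0.39, 2 / 3 levels | Loss (points) | Size under null, 2 / 3 levels |
|---|---|---|---|---|
| 1.0 | 0.381 / 0.378 | 92.2% / 92.2% | 0.1 | 5.4% / 5.6% |
| 1.5 | 0.384 / 0.375 | 91.8% / 92.3% | 0.6 | 5.2% / 5.6% |
| 2.0 | 0.396 / 0.374 | 90.5% / 92.3% | 1.9 | 4.8% / 5.7% |
| 3.0 | 0.425 / 0.377 | 87.0% / 91.9% | 4.9 | 3.8% / 5.6% |

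Losses are taken from unrounded values.

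**4. Other response mixes.**
- 10/30/60%: losses 0.1, 0.5, 1.4 and 4.1 points; pooled power at ratio 3 is 88.1% and size 3.7%.
- 25/40/35%: losses 0.0, 0.6, 1.4 and 5.1 points; pooled power at ratio 3 is 87.1% and size 4.0%.

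A separate simulation of the same four ratios gave pooled against three-level power of 92.0/91.6/90.9/87.8% against 92.1/92.5/92.8/92.2%, and pooled size of 5.6/5.4/5.1/3.6%.

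**5. Where the power goes.** At ratio 3 the mean standard error of the log hazard ratio is 0.287 pooled and 0.294 with three levels, so pooling does not widen it. The loss comes from the estimate: ln 0.425/0.287 = −2.98 against ln 0.377/0.294 = −3.32.

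**The case against.** The strongest reply is that this is a defensible modelling choice. All three covariates are dichotomised, the model is prespecified and sparing for 55 events, and nothing obliges stratification factors to enter at the levels used for randomisation. The pooled test is valid. All of that stands, and it is why the point is minor. It does not explain why response is split one way for balance and another for adjustment.

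Second, the harm depends on a VGPR–PR difference that the protocol does not give; section 14.1 itself says that there are no PFS data yet after this induction. This also stands. With no difference there is no loss, and the larger losses need a ratio near 3.

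Third, part of the three-level model's advantage is its slightly higher size, which is small-sample Wald behaviour. By a normal approximation at ratio 2, a size of 5.65% corresponds to a critical value of 1.907 instead of 1.960. Restoring 5% takes 92.3% to Φ(1.428 − 0.053) = 91.5%, about 1 point above the pooled model. The same step at ratio 3 gives Φ(1.395 − 0.052) = 91.0%, still 4 points above 87.0%. So the moderate-case gain is smaller than the raw figures suggest.

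Fourth, centre is also a minimisation factor and is also absent from the model. With 94 patients that omission can reasonably stay.

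A reader might infer that pooling endangers the type I error in the harmful direction, or that it necessarily biases the trial and breaks its power. Neither is supported. The size of the pooled test moves down as the VGPR–PR difference grows, and planned power survives up to a ratio of 2.

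**Conclusion.** The mismatch between sections 14.2.1 and 15.2.2 is real, concerns the sole confirmatory test, and cannot be corrected in the SAP. Its consequence is conditional and mostly small: no loss if VGPR and PR share the same PFS, under 1 point of power at a PR-vs-VGPR hazard ratio of 1.5, and about 2 points or less at 2 with 90% kept. At 3 the loss is about 4–5 points, to about 87–88%, with the pooled test running at about 3.6–4%. The estimated hazard ratio there is about 0.42 instead of about 0.375.

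These sizes rest on the assumed response mixes, prognostic effects and minimisation settings listed above; the direction does not. No disadvantage of aligning the factor was found beyond one extra parameter. This is a free improvement of minor severity and does not threaten the trial's validity. The 55 events and 94 patients are unaffected.

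**What to change.** By protocol amendment before unblinding, change the response term in section 14.2.1 to (s)CR vs VGPR vs PR, entered as two indicators, to match section 15.2.2. Leave ISS and age as they are. Centre may stay out of the model given 94 patients; one sentence saying so would complete the account. If the sponsor prefers to keep two levels, 14.2.1 should state why VGPR and PR are pooled.

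The cost is one bracket of text and one extra parameter for 55 events. Sample size, event target and data collection do not change, because three-level response is already used at randomisation.

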14.2.2 Toxicity analysis

The analysis of treatment toxicity will be done primarily by tabulation of the incidence of adverse events CTCAE grade 2 or more by induction cycle, and also for maintenance and placebo. Data from all subjects who receive any study drug will be included in the safety analyses. In the by-subject analysis, a subject having the same event more than once will be counted only once. Adverse events will be summarized by worst CTCAE grade.

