9.2 Maintenance treatment with ixazomib citrate or Placebo maintenance

9.2.1 Treatment schedule

After the response evaluation of the last ixazomib citrate -thalidomide-low dose dexamethasone cycle patients will be randomized. In randomized patients, maintenance treatment with either ixazomib citrate or placebo will be started within a maximum of 12 weeks after start of the last ixazomib citrate - thalidomide-low dose dexamethasone cycle, at a dose of 4 mg on days 1, 8, and 15 of a 28-day cycle.

Maintenance cycles will be repeated at 28-days intervals until progression or when a medical condition occurs that requires discontinuation of the treatment.

Agent	Dose/day	Route	Days
Ixazomib citrate or	4 mg*	p.o	1, 8 and 15
placebo			

^{*}or at the dose level during induction therapy in case dose reductions were required during induction therapy

Response evaluation will take place as described in chapter 10.

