12.2 Adverse event

12.2.1 Reporting of adverse events

Adverse events will be reported from the first study-related procedure until 30 days following the last dose of any drug from the protocol treatment schedule or until the start of subsequent systemic therapy for the disease under study, if earlier.

Adverse events occurring after 30 days should also be reported if considered at least possibly related to the investigational medicinal product by the investigator.

Adverse Events have to be reported on the Adverse Events CRF. Adverse Events will be scored according to the NCI Common Terminology Criteria for Adverse Events, version 4.0 (see appendix E). The investigator must determine both the intensity of the event and the relationship of the event to study drug administration.

Pre-existing conditions will be collected on the baseline concomitant diseases CRF, i.e. active (symptomatic) diseases of CTCAE grade ≥ 2 diseases under treatment, chronic diseases and long term effects of past events as present at the time of baseline assessment.

All Adverse Events have to be reported, with the exception of.

- A pre-existing condition that does not increase in severity; the pre-existing condition should be reported on the baseline concomitant diseases CRF
- ◆ AE's of CTCAE grade 1, however polyneuropathy grade 1 has to be reported
- An abnormal laboratory value that does not lead to discontinuation or delay in treatment, or dose modification, or therapeutic intervention, and is not considered by the investigator to be a clinically significant change from baseline
- Relapse/progression of the disease under study; complications as a result of disease progression remain reportable Adverse Events

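### Protocol 14.2.2 makes crude adverse-event incidence the main toxicity summary for maintenance although time at risk follows PFS, so the planned benefit would by itself raise the ixazomib figures

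*Protocol*

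**What the plan says.** Section 14.2.2 states that the toxicity analysis "will be done primarily by tabulation of the incidence of adverse events CTCAE grade 2 or more". The breakdown is per cycle for induction; ixazomib and placebo maintenance are then named without any time unit. The counting rule for the by-subject analysis is that "a subject having the same event more than once will be counted only once", and events are also to be summarized by worst CTCAE grade. Induction therefore has a time axis. For maintenance and placebo, sections 14.2 and 14.3 state no cycle breakdown, person-time rate or common time window.

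Three other sections determine how long each patient is observed for adverse events:

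- Section 9.2.1: "Maintenance cycles will be repeated at 28-days intervals until progression or when a medical condition occurs that requires discontinuation of the treatment".
- Section 12.2.1: AEs are reported "until 30 days following the last dose of any drug from the protocol treatment schedule or until the start of subsequent systemic therapy", whichever comes first; the therapy meant is one against the myeloma. Later events are reported only if at least possibly related to the investigational product.
- Section 14.1: the plan assumes "median PFS in the no-maintenance arm = 10 months", 26 months with ixazomib, and a hazard ratio of 0.39.

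On grade, section 12.2.1 exempts from reporting "AE's of CTCAE grade 1, however polyneuropathy grade 1 has to be reported". Section 6 lists toxicity, polyneuropathy in particular, as the first secondary objective for both induction and maintenance.

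**The concern.** A crude proportion counts how many patients ever had an event while observed. Here the length of observation depends on the primary endpoint. If ixazomib delays progression, its patients take capsules for longer, stay longer in the AE window and collect more events, even if the drug adds no toxicity in any month of treatment. A reader comparing the two maintenance columns would then attribute to the drug what is partly a longer time at risk. Section 5.3 says the data may be used to design a phase III trial with or without ixazomib maintenance, so tolerability against placebo is an output that will be used.

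A smaller point concerns polyneuropathy. It is the one event collected from grade 1, while the main tabulation starts at grade 2.

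**Working it through.** **Inputs from section 14.1.** Median PFS 10 months on placebo; HR 0.39; uniform accrual over 18 months plus 12 months of follow-up; two-sided alpha 0.05; power 0.90; 47 patients per arm; 55 events.

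**Assumptions not in the documents.** Exponential PFS; treatment stops only at progression or data cutoff; AE hazard h constant and equal in the two arms, with h = 1 to 5% per month as the main range.

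**Reproducing the plan.** The Freedman formula gives (1.960 + 1.282)² × (1.39/0.61)² = 54.6, so 55 events, as stated. The monthly progression hazards are λ = ln 2/10 = 0.0693 on placebo and 0.39 × 0.0693 = 0.0270 on ixazomib. With follow-up uniform on 12 to 30 months, the probability of an event at rate r is

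p(r) = 1 − (e^(−12r) − e^(−30r)) / (18r).

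This gives 0.751 and 0.428, with mean 0.589. Then 55/0.589 = 93.3, which leads to 94 patients, as stated.

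**Mean exposure at the final analysis** is p(λ)/λ:

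- placebo: 0.7513/0.0693 = 10.8 months
- ixazomib: 0.4276/0.0270 = 15.8 months
- ratio 1.46

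Adding the 30-day window gives 11.6 and 16.2 months, ratio 1.40.

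**Crude incidence with equal AE hazards** is h/(h+λ) × p(h+λ). At h = 0.02:

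- placebo: 0.224 × 0.830 = 18.6%
- ixazomib: 0.425 × 0.616 = 26.2%

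| h per month | Placebo | Ixazomib | Ratio | Ratio with 30-day window |
|---|---|---|---|---|
| 0.01 | 10.0% | 14.4% | 1.43 | 1.38 |
| 0.02 | 18.6% | 26.2% | 1.41 | 1.36 |
| 0.03 | 25.9% | 36.0% | 1.39 | 1.34 |
| 0.05 | 37.8% | 51.0% | 1.35 | 1.30 |

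By construction the event rate per patient-month has ratio 1.00 in every row. In patients, the excess runs from 0.043 × 47 = 2.0 to 0.132 × 47 = 6.2. At 2% per month it is 0.076 × 47 = 3.6.

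**Sensitivity.**

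- PFS effect: the exposure ratio falls from 1.46 to 1.27 at HR 0.6, 1.12 at HR 0.8 and 1.00 at HR 1.
- Timing of events: with the 30-day window, the crude ratio is about 1.03 if AEs arise only in the first 3 months, 1.07 to 1.08 for the first 6 months, and 1.16 to 1.19 for the first 12 months.
- Extra stopping for toxicity on ixazomib alone: at 2% per month the exposure ratio is 1.21, and at about 4% per month the gap is gone.

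**Which alternatives remove the effect.** Cumulative incidence with end of treatment as a competing event does not. At h = 0.02 and time t it equals h/(h+λ) × (1 − e^(−(h+λ)t)):

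| t (months) | Placebo | Ixazomib | Ratio |
|---|---|---|---|
| 12 | 14.7% | 18.3% | 1.25 |
| 24 | 19.8% | 28.8% | 1.46 |
| 30 | 20.9% | 32.2% | 1.54 |

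The later ratios exceed the crude 1.41, because progression-driven stopping carries the exposure difference into the estimate.

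A patient-month rate removes the effect when the hazard is constant. If events cluster early it overcorrects. With a hazard of 3% per month in the first 3 months only, the crude figures are 8.2% and 8.5%. Dividing by the whole observed time gives 0.082/11.6 = 0.0071 and 0.085/16.2 = 0.0052 per month, ratio about 0.74. Incidence per cycle among patients still on treatment depends on neither pattern.

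**The case against.** The strongest reply is that this belongs to the SAP. Section 14.2.2 says only that tabulation is the *primary* method, 14.2.4 promises a detailed SAP, and exposure-adjusted rates are routine there. It is true that nothing in the protocol forbids the extra tables. But the protocol is not silent: it names crude incidence as the main summary and gives a time axis to induction only. That choice can be judged as it stands.

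Four stronger readings are tempting and are not supported.

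- *A harmless drug would look toxic.* A reader might infer this without conditions. It requires a PFS benefit near the planned size, AEs that keep arising during maintenance, and little stopping before progression. Section 9.2.1 allows stopping for a medical condition, and enough toxicity stopping on ixazomib would close the gap.
- *The trial would produce a false safety signal.* Section 14.2.2 states no test, and 14.2.4 makes every analysis but the primary one hypothesis-generating. At 2% per month the 7.6-point gap compares with a 95% half-width of about 17 points at 47 per arm. Even if someone tested it, p < 0.05 would occur in about 9 to 25% of trials at 1 to 5% per month.
- *Grade 1 polyneuropathy is lost from the analysis.* The worst-grade summary has no grade floor, so it may well appear there. What is missing is a statement that it will.
- *The benefit-risk judgement rests on this table.* Discontinuation for toxicity, serious adverse events, second primary malignancies and quality of life by arm also inform it.

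**Conclusion.** The point holds as a conditional, descriptive distortion. If PFS differs as planned, mean exposure is about 10.8 against 15.8 months. With equal and constant AE hazards of 1 to 5% per month, crude incidence would then be 1.35 to 1.43 times higher on ixazomib, or 1.30 to 1.38 times with the 30-day window. The hazard range is an assumption, since the protocol gives no figure. The effect shrinks with a smaller PFS benefit, with events that cluster early or with toxicity stopping, and is nil at HR 1. It affects neither the primary analysis nor any planned test. This is a cheap improvement to make rather than an error that undermines the trial.

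**What to change.** In section 14.2.2, keep the crude table and add the following for the maintenance phase, by arm:

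- event rates per patient-month on treatment, with the 30-day window included in both numerator and denominator;
- incidence per maintenance cycle among patients still on treatment, which also shows whether events cluster early. After the first year, two-cycle intervals would match the 8-weekly visits in section 10.1.

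Either addition helps, but the two together cover both constant and early-clustering hazards. Do not rely on cumulative incidence with end of treatment as a competing event to correct for exposure.

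Also add a sentence that polyneuropathy is tabulated from grade 1, in line with section 12.2.1.

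The cost is a few more tables. Section 16.1 already lists timing of treatment and adverse events among the CRF data; AE onset dates are implied rather than named, so their presence should be confirmed. Section 14.2.4 permits the change because the primary analysis is untouched.

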- To determine toxicity, polyneuropathy in specific, during induction treatment and maintenance treatment with ixazomib citrate or placebo
- ♦ To determine progression free survival and overall survival from registration
- ♦ To compare the efficacy between maintenance treatment with ixazomib citrate versus placebo determined as overall survival from randomization
- To determine the efficacy of maintenance therapy determined as an improvement in response during maintenance treatment with ixazomib citrate or placebo
- ♦ To determine efficacy of induction therapy determined as time to response
- ♦ To determine feasibility, defined as discontinuation rate due to toxicity, during induction treatment and maintenance treatment with ixazomib citrate or placebo
- To determine time to next treatment
- To determine PFS on second line therapy
- To determine Quality of Life during induction treatment and maintenance therapy with Ixazomib or placebo
- To identify clinical, imaging-related and molecular markers prognostic and predictive for outcome and toxicity
- To establish second primary malignancies (SPM)

7 Study design

This is a multicenter phase II clinical trial, with upfront registration and late double-blind, placebocontrolled, maintenance randomization. Details of all treatments (dose and schedule) are given in section 9 and appendix F, G and H.

- 1. Patients will be registered, and then they will be treated with 9 cycles of induction therapy* with ixazomib citrate— thalidomide low dose dexamethasone;
- 2. After induction, patients eligible for randomization will be randomized double-blind between maintenance treatment with ixazomib citrate versus placebo.

The primary objective of this trial is to assess whether maintenance with ixazomib citrate improves PFS (calculated from date of randomization) as compared to placebo. This is used for the sample size calculation. This trial is therefore a superiority trial.

* Randomization and subsequent start of maintenance therapy is allowed after a minimum of 6 induction cycles as described in 8.2.1.

8 Study population

All eligible patients have to be registered before start of treatment. After the induction treatment patients will be randomized.

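### Section 14.2.2 sets no cycle split or common time base for maintenance versus placebo toxicity, although adverse-event observation largely follows time on treatment

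*Protocol*

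**What the plan says.** Section 14.2.2 describes the main toxicity analysis as a "tabulation of the incidence of adverse events CTCAE grade 2 or more by induction cycle, and also for maintenance and placebo". In the by-subject analysis, "a subject having the same event more than once will be counted only once", and events are summarised by worst grade. The cycle split is attached to induction. For the randomised phase the section names the two arms and gives no cycle split, person-time denominator or common time window.

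Three other places determine how long each patient is observed for adverse events:

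- **Collection window (section 12.2.1).** Events are reported "until 30 days following the last dose of any drug from the protocol treatment schedule", or until the next systemic therapy if that is earlier. There is an exception: "Adverse events occurring after 30 days should also be reported if considered at least possibly related to the investigational medicinal product by the investigator". Section 12.6 separately follows second primary malignancies to 8 years after registration.
- **Length of maintenance (section 9.2.1).** "Maintenance cycles will be repeated at 28-days intervals until progression or when a medical condition occurs that requires discontinuation of the treatment".
- **Planned effect (section 14.1).** "An improvement of median PFS from 10 to 26 months with ixazomib citrate-maintenance equals a hazard ratio of 0.39".

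**The concern.** By-cycle tabulation in induction compares like periods of exposure. The randomised phase has no such protection. One incidence per arm, counting each subject once, depends on the event rate and on how long each patient is watched. For most adverse events that time is close to time on treatment, which ends at progression. Progression is the main component of the primary endpoint, so a successful trial would itself produce unequal windows.

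The comparison matters because toxicity during ixazomib or placebo maintenance, polyneuropathy in particular, is a secondary objective (section 6). Section 5.3 also says the results may inform a phase III design. A reader of the table could take a difference in observation time for a difference in toxicity, or miss a real difference because the windows hide it.

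**Working it through.** **Inputs from section 14.1:** control median PFS 10 months, HR 0.39, uniform accrual over 18 months plus 12 months' follow-up, two-sided 5% level, 90% power, 47 patients per arm. **From section 12.2.1:** a 30-day tail, taken as 1 month.

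**Assumptions:** exponential PFS; treatment stops only at progression, death or data cut-off; the adverse-event rate r per month is constant and the same in both arms. The protocol gives no value for r, so a range is shown.

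**1. The plan's own figures.** Monthly PFS hazards are λ0 = ln 2/10 = 0.0693 and λ1 = 0.39 × 0.0693 = 0.0270.

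- Events (Freedman): (1.960 + 1.282)² × (1.39/0.61)² = 54.6, so 55, as stated.
- Event probability with cut-off C uniform on 12 to 30 months: 1 − [exp(−12λ) − exp(−30λ)]/(18λ) = 0.751 (placebo) and 0.428 (ixazomib), mean 0.589.
- 55/0.589 = 93.3, rounded up to an even 94, as stated.

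**2. Mean time on maintenance.** Event probability divided by hazard: 0.7513/0.0693 = 10.8 months and 0.4276/0.0270 = 15.8 months, a ratio of 1.46.

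**3. Mean adverse-event window.** E[min(T + 1, C)] = 1 + average over C of [1 − exp(−λ(C − 1))]/λ = 11.6 months and 16.2 months.

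**4. Incidence at identical rates.** Incidence = 1 − exp(−r) × average over C of [λ + r·exp(−(λ + r)(C − 1))]/(λ + r).

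| Rate per month (assumed) | Placebo | Ixazomib | Excess (points) |
|---|---|---|---|
| 1% | 10.7% | 14.7% | 4.0 |
| 2% | 19.8% | 26.9% | 7.1 |
| 4% | 34.5% | 45.3% | 10.9 |
| 5% | 40.3% | 52.3% | 12.0 |
| 10% | 60.4% | 73.8% | 13.5 |

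(The excess is taken before rounding.)

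**5. Smaller PFS effect.** Over the same range of r, the excess is 2.4 to 8.2 points at HR 0.60, 1.1 to 3.8 points at HR 0.80, and zero at HR 1.0.

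**6. Extra early stopping on ixazomib.** Replace λ1 by λ1 + x in step 4. At r = 2%, x = 2% per month gives 19.8% versus 23.1%. At x = λ0 − λ1 = 0.0693 − 0.0270 = 0.042 the windows are equal and the excess is zero for any r. Above about 4.2% per month the sign reverses.

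**7. Is a rate per patient-month a safe replacement?** Suppose the hazard is 10% per month for the first 3 months and zero afterwards, the same in both arms (assumed, no tail). Incidence = 0.1/(0.1 + λ) × [1 − exp(−3(0.1 + λ))] = 23.5% versus 24.9%, almost unbiased. Events per 100 patient-months are 23.52/10.84 = 2.17 and 24.95/15.82 = 1.58. That ratio of 0.73 is a spurious 27% reduction on ixazomib. The person-time rate has its own artefact when events cluster early.

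**The case against.** **This is detail for the SAP.** Section 14.2.4 leaves the detail of the analyses to a SAP, which is not shown, and lets it depart from the protocol outside the primary analysis. Section 14.2.2 never says that incidence is unadjusted or excludes a cycle split in maintenance. That part stands: reading the text as one figure per arm is the natural reading, but an inference. The protocol is not silent, however. It names its main toxicity summary and counting rule, and it specifies a cycle split for the single-arm phase but not for the randomised one.

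**A reader might infer that events are collected only on treatment.** They are not: there is the 30-day tail, later possibly related events are reported, and second primary malignancies are followed to 8 years. None of this equalises the windows for general adverse events.

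**A reader might infer that the table must exaggerate ixazomib toxicity.** That requires ixazomib patients actually to be treated longer. Sections 9.2.1 and 11.1 allow stopping for medical conditions, toxicity, non-compliance and refusal, and step 6 shows that enough of this cancels or reverses the effect.

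**A reader might infer that the feasibility objective shares the flaw.** Section 6 states it as "To determine feasibility, defined as discontinuation rate due to toxicity, during induction treatment and maintenance treatment with ixazomib citrate or placebo", but no passage says how that rate is estimated, so no method is there to criticise.

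**A reader might infer that the trial's only safety comparison, and its benefit-risk conclusion, are distorted.** Second primary malignancies and quality of life are also assessed, and section 14.2.4 makes everything except the primary analysis hypothesis-generating. Sampling error is also larger than the artefact: with 47 per arm, the 95% half-width for 34.5% versus 45.3% is 1.96 × √(0.345 × 0.655/47 + 0.453 × 0.547/47), about 20 points. The artefact is nevertheless systematic, and replication would not remove it.

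**Conclusion.** The point holds in limited form. Followed as written, section 14.2.2 would compare the randomised arms over observation windows that differ whenever time on treatment differs, and the design expects it to differ. Under the protocol's assumptions, with treatment ending only at progression, death or cut-off, identical event rates would produce an apparent excess of 4 to 13.5 points on ixazomib across assumed rates of 1% to 10% per month. At 4% per month it is about 11 points. Size and direction depend on the true PFS effect, on stopping for other reasons and on the timing of events. The matter concerns the reading of a descriptive secondary comparison. The primary PFS test is unaffected, and its 55 events and 94 patients reproduce.

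**What to change.** In section 14.2.2, for the randomised phase:

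1. Tabulate adverse events by 28-day maintenance cycle, or by fixed period, among patients starting that cycle, as is done for induction. Show the number at risk, since later cycles compare only patients still on treatment. Alternatively, give cumulative incidence at fixed times, with progression or end of treatment as a competing event shown beside it.
2. Keep the overall incidence, with exposure time per arm printed next to it.
3. Rates per patient-month may be added as a supplement, stating that they assume a roughly constant hazard. They should not be the main replacement (step 7).
4. Present discontinuations for toxicity by arm on the same time base. The protocol states no method for these, so this is an addition and not a correction.

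The cost is some wording and a few extra tables. Section 16.1 already puts timing and dosage of treatment on the CRF, so no new data are needed.
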